Primary and secondary outcomes will be evaluated at baseline, 4 follow-up points during the SMA intervention, and 3 and 6 months after the final group visit. A 3-month interval for SMA and assessment was chosen to correspond to standard clinical follow up visit schedule. Participant data will be matched by age, race, insurance status, duration of diabetes, in the routine follow up model, in order to evaluate the impact of SMA on the outcomes of interest.

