### **3.4 Secondary Outcome Measure(s)**

Secondary outcomes will include CGM metrics and chart review that can be used to assess effects on glycemic control, and survey measures designed to explore potential psychosocial benefits, including changes in self-management skills, self-efficacy, treatment satisfaction, and diabetes related quality of life. We will look at differences in the following measures from baseline to completion of the SMA intervention, as well as 3 and 6-months after completion of the SMA intervention: 1) CGM time in range from 70-180 mg/dL (TIR), 2) time below range (< 70 mg/dL) (TBR), 3) time above range ( $\geq$  180 mg/dL) (TAR), 4) mean sensor glucose, 5) coefficient of variation (CV) of glucose, 6) CGM wear time, 7) episodes of DKA, 8) episodes of severe hypoglycemia, 9) ED visits, hospital admissions, 10) A1c, 11) qualitative measures exploring self-management, satisfaction, health related quality of life as measured with the following validated questionnaires (T1DAL, DSMP, SEDS, C-PAID, CGM Benefits and Burdens scale).

CGM time in range from 70-180 mg/dL (TIR) has been correlated with A1c values, which have classically been used as primary outcomes in T1D studies because of their association with microvascular complications. This connection to long-term complications also makes TIR a better primary outcome measure than survey measures because this data has greater potential to alter real-world prescribing practices than patient perceptions captured by questionnaire. We have chosen to focus on TIR rather than A1c because of the propensity for A1c variation in Non-Hispanic Black youth who also have a higher propensity for hemoglobin variants.

Additional CGM derived measures of glycemic control are commonly used outcomes in studies of T1D technology. A1c has been included because it has classically been considered the gold standard. The acute complications of T1D being examined are also frequently used in T1D studies. The survey measures exploring quality of life are among the most widely accepted outcome measures in their specific topic areas.

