#### Follow up SMA at 3, 6, 9, and 12-months

Follow up SMA will be scheduled 3, 6, 9 and, 12 months from the initial group visit. Data will be collected from routine clinical care, including height, weight, BMI, and a point of care fingerstick A1c. Survey measures will be completed again as described previously. CGM data will be analyzed for the 14 days preceding each visit. Chart review from the time of the initial baseline visit will be conducted to assess the incidence of DKA, severe hypoglycemia, ED visits, and hospital admissions. Details obtained from the chart review will be confirmed with participants. Data from the CGM will be obtained through online software used to securely query these devices for routine clinical care (Dexcom Clarity).

Discussions and education guided by the facilitators will focus on issues that have been described in the literature as potential barriers to CGM use and adherence. Recurrent alerts and alarms can result in alarm fatigue, and falsely low glucose readings and sensor or transmitter failures have been cited as reasons for discontinuing CGM use. The continuous nature of CGM data has been shown to place significant demands on patients and their families, and to create stress related to the constant need for

diabetes-related attention. Follow up visits will focus on optimized use of CGM alarms and prevention of alarm fatigue. Psychologists and CDCES will discuss strategies to cope with the on-body presence and potential embarrassment resulting from CGM wear and to optimize parent-child communication surrounding CGM. Nutritionists will highlight the impact of different foods on glycemic trends and discuss strategies to optimize control. SMA will also allow ample opportunity to jointly review deidentified CGM reports and how to effectively interpret data and make management changes in response to CGM data, empowering patients and families to improve self-management and reduce stress related to CGM use. Active participation in discussions and group exercises will continue to strengthen the community feeling and social support network within the SMA group. Any participant that chooses to discontinue CGM during the 12 month study period will wear a blinded CGM 10 days prior to the follow up visits to allow for complete data collection.

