## **6.4 Description of Study Procedures/Evaluations**

### **Study Visits**

All SMA appointments will be scheduled at the time that consent is obtained. Biometric data (height, weight, BMI, A1c) will be obtained as part of routine care. Data from 14 days prior to the visit for the CGM will be obtained through online software used to securely query these devices for routine clinical care (Dexcom Clarity). Secure REDCap surveys will be sent to participants via email 1 week before their visit (including the T1DAL, DSMP, SEDS, PAID, CGM Benefits and Burdens, and an SMA evaluation for patients; and for parents: P-T1DAL, P-DSMP, P-SEDS, and P-PAID, CGM Benefits and Burdens, and SMA evaluation). If the surveys have not been completed at the time of the visit participants will be given the option to complete the measures using an iPad or paper surveys in clinic at the time of their visit.

Prior to the study visit, chart review will be conducted to assess the interval incidence of DKA, severe hypoglycemia, ED visits, and hospital admissions. This will be conducted in accordance with the HIPAA rules. Information obtained through chart review will be

corroborated with patients during study visits to ensure accuracy. Biometric data, CGM data obtained from Clarity, and A1c values will be provided to participants as part of routine clinical care. The results from the battery of questionnaires will not be provided to patients.

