### **8.4 Description of Statistical Methods**

#### **General Approach**

Descriptive measures will be used to summarize participant demographic information. P-values and confidence intervals will be two-tailed. Covariates will be pre-specified. Tests to assess normality will be performed and data transformation or non-parametric analyses will be used when necessary.

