The incidence of DKA and DKA event rate per 100 person-years, incidence of severe hypoglycemia and severe hypoglycemia event rate per 100 person-years, incidence of ED visits and ED visit event rate per 100 person-years, incidence of hospital admissions and hospital admission event rate per 100 person-years, will also be compared using linear longitudinal regression analysis. Results will be reported as least-squares means (LSMEANS) with standard errors. Casewise deletion will be used to handle missing data.

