### **Tabulation of Individual participant Data**

Individual participant data will be listed by measure and time point.

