## **8.5 Sample Size**

As this is a pilot study, we plan to enroll up to 20 parent-child dyads. We anticipate low dropout rates, but do plan to enroll new subjects to keep the total number of subjects at up to 20 in case of attrition. If there is a sufficient number of new subjects enrolled to replace those that drop out, a new SMA group will be created so that newly enrolled subjects will be able to start the intervention from the baseline visit.

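### Linear-model means with standard errors give poor intervals for the period rates of DKA, severe hypoglycemia, ED visits and admissions if events are few, and the baseline for these events is undefined

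*Combined protocol and SAP*

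**What the plan says.** Under Analysis of the Secondary Efficacy Endpoint(s), section 8.4 takes the incidence and the rate per 100 PY of DKA, severe hypoglycemia, ED visits and hospital admissions and states that these "will also be compared using linear longitudinal regression analysis. Results will be reported as least-squares means (LSMEANS) with standard errors". It names no count model, person-time offset or exact interval. Section 8.1 states that no separate SAP will be written, so section 8.4 is the only place for the method.

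Two general provisions bear on this. The General Approach says "Tests to assess normality will be performed and data transformation or non-parametric analyses will be used when necessary" and makes confidence intervals two-tailed. The tabulation paragraph says "Individual participant data will be listed by measure and time point".

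On size, section 8.5 says "As this is a pilot study, we plan to enroll up to 20 parent-child dyads". Section 4 gives 12 months of SMA visits and 6 months of observation in a single group.

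On baseline, section 3.4 says "We will look at differences in the following measures from baseline to completion of the SMA intervention", and its list includes these four events. Section 2.2 says "Primary and secondary outcomes will be evaluated at baseline, 4 follow-up points during the SMA intervention". On ascertainment, section 6.3 says "Chart review from the time of the initial baseline visit will be conducted to assess the incidence of DKA, severe hypoglycemia" and section 6.4 says "Prior to the study visit, chart review will be conducted to assess the interval incidence of DKA, severe hypoglycemia, ED visits, and hospital admissions".

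**The concern.** Event counts in 20 children may be mostly zeros. A symmetric interval around the mean of such data can include impossible negative rates and end below rates that the data do not rule out. For acute complications that is the unhelpful direction, because the table would look more reassuring than 20 PY can justify. The normality fallback does not cure this: transforming mostly-zero counts does not make them normal, and a rank test gives no rate with an interval.

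The second issue needs no assumed rate. A baseline event rate needs a stretch of time before the first SMA, and none is given. Any reported change from baseline would depend on whichever look-back the chart reviewer happened to use.

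**Working it through.** **Inputs.** 20 children (section 8.5); 12 + 6 months (section 4), so 20 x 1 = 20 PY and 20 x 0.5 = 10 PY with full follow-up. Two-sided intervals (General Approach); the 95% level is assumed. The documents give no event rate, so 5 to 40 per 100 PY is an assumed range. There is no figure in the plan to reproduce.

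**Linear model.** Random intercept per child, six quarters, period as factor; SMA-year LSMEAN = mean of quarters 1-4, interval = LSMEAN ± 1.96 SE, scaled to per 100 PY.

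Example, one event in the SMA year and none in follow-up:
- Mean = 1/80 per child-quarter; x 400 = 5.0 per 100 PY.
- Residual sum of squares = 1 - 1/20 = 0.95 on 6 x 19 = 114 df, so s² = 0.00833 (between-child variance is estimated as 0).
- SE = 400 x sqrt(0.00833/80) = 4.08.
- Interval = 5.0 ± 1.96 x 4.08 = -3.0 to 13.0.

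**Exact Poisson.** Limits = chi-square quantiles on 2k and 2k+2 df, divided by 2 and by 20 PY. For k = 1: 0.1 to 27.9.

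SMA-year limits per 100 PY, with each event in a different child:

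| Events, SMA year / follow-up | Linear | Exact Poisson |
|---|---|---|
| 0 / 0 | 0 to 0 | 0 to 18.4 |
| 0 / 1 | -8.0 to 8.0 | 0 to 18.4 |
| 1 / 0 | -3.0 to 13.0 | 0.1 to 27.9 |
| 1 / 1 | -6.3 to 16.3 | 0.1 to 27.9 |
| 2 / 1 | -3.9 to 23.9 | 1.2 to 36.1 |
| 4 / 2 | 0.4 to 39.6 | 5.4 to 51.2 |
| 8 / 4 | 13.0 to 67.0 | 17.3 to 78.8 |

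**Simulated behavior of the SMA-year interval**, constant rate, in % of trials (Poisson / overdispersed, gamma-Poisson with shape 1):

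| Rate per 100 PY | Linear coverage | Lower limit negative | SE = 0 | Exact coverage |
|---|---|---|---|---|
| 5 | 78 / 76 | 73 / 72 | 22 / 24 | 98 / 98 |
| 10 | 89 / 88 | 77 / 78 | 5 / 6 | 98 / 98 |
| 20 | 93 / 91 | 52 / 58 | under 1 | 96 / 94 |
| 40 | 94 / 91 | 14 / 25 | under 1 | 97 / 93 |

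The upper limit is too low in 22.4% / 23.9% of trials at 5 and in 9.9% / 11.5% at 10. The SE is 0 only when no event occurs in any modelled period. For Poisson counts that has probability exp(-0.05 x 30) = 22.3% at 5 and exp(-0.10 x 30) = 5.0% at 10. So nearly all misses at 5, and about half at 10, are trials without any event. Among trials with at least one event, coverage is 99.6% at 5 and 94% at 10.

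**The comparison.** In the same model, the SMA-year minus follow-up difference covers 97 / 96 / 96 / 95% at constant rates of 5 / 10 / 20 / 40. At constant rates an all-zero trial counts as covered, because 0 to 0 contains the true difference of 0. With a true halving, coverage is 95-96% for 20 to 10, 96-97% for 40 to 20, and about 85-86% for 10 to 5. In that last case no event occurs with probability exp(-(0.10 x 20 + 0.05 x 10)) = exp(-2.5) = 8.2% under Poisson, more than half of the roughly 14% of misses.

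**Baseline, side by side.** Section 3.4 needs a baseline value for these events, and section 2.2 says that secondary outcomes are evaluated then. Section 6.3 starts chart review at the baseline visit and moves forward. The interval in section 6.4 has a natural length between visits but none before the first SMA. The Protocol Summary describes the same outcomes as differences over the SMA and follow-up periods, which can be read as needing no pre-SMA period.

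**The case against.** Four points on the other side have weight.

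- A reader might infer that the linear model invalidates the comparison itself. The check does not support that: the between-period difference is mostly near nominal and falls clearly short only at very low, falling rates.
- A reader might also infer that a period without events always shows an SE of 0. In a model pooled over periods this happens only if no event occurs at all. The listings and the rates per 100 PY would then show plainly that nothing happened.
- The plan promises SEs, and ± 1.96 SE is a construction put on them. In a single-period calculation the linear SEs for 1, 2 and 3 events are 5.0, 6.9 and 8.2 per 100 PY, against Poisson SEs (100 x sqrt(k)/20) of 5.0, 7.1 and 8.7. The SE itself is therefore close, and the symmetric limit is what fails. Since the General Approach foresees confidence intervals, that limit still matters.
- Event rates are unknown for each outcome. A frequent one, possibly ED visits, could be little affected.

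On baseline, the Protocol Summary's wording and the forward chart review are compatible with each other. The gap is therefore a conflict with sections 3.4 and 2.2, which one clarifying sentence can settle.

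**Conclusion.** The point stands in limited form. If events occur at about 10 per 100 PY or less, the period rates of these four outcomes would be reported with error bars that usually include negative values and too often end too low. SMA-year coverage is about 78% at 5 and 89% at 10 per 100 PY; at 20 to 40 the shortfall is modest (91-94%). The comparison between periods is not generally at fault. These sizes rest on the assumed rates, full follow-up of 20 children and one reasonable reading of an incompletely specified linear model.

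The baseline contrast cannot be computed as written, whatever the rates are, and the passages must be reconciled.

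Severity is minor. These are secondary outcomes outside hypotheses 2a-2c, and the primary feasibility and acceptability result is unaffected. Section 2.4 expects the study to inform later randomized trials, but nothing says that these event rates would be carried into them.

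**What to change.** **Section 8.4.** For these four outcomes, replace the linear LSMEANS with event counts, number of children affected, person-time and rates by period (SMA year, 6-month follow-up), with exact Poisson 95% intervals, labelled descriptive. Give a rate ratio only if events occur in both periods, and label it exploratory: it has no finite estimate when a period has no events, and clustered SEs are unreliable with 20 children.

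**Sections 3.4, 6.3 and 6.4** (with section 2.2 aligned). Do one of two things:
- Delete the baseline contrast for these events. This is the cheaper choice.
- Define one fixed pre-SMA chart look-back that starts after diagnosis, since section 5.2 admits children with only 1 year of diabetes. State that before/after differences are open to regression to the mean, because children are selected on an A1c above 8% in the preceding year.

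**Cost.** Wording only, plus one extra chart review if the look-back is kept. The intervals become wider, and the exact interval undercovers slightly (about 93% at 40 per 100 PY) if children differ strongly. A look-back would rely on caregivers for events treated elsewhere. It would add description and very little inference: power to detect a halved rate with 20 PY in each period is 0.7%, 4.6% and 13.4% at 10, 20 and 40 per 100 PY (conditional exact test, two-sided 0.05).

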### **Baseline Descriptive Statistics**

Age, gender, race, duration of diabetes, height, weight, BMI, and A1c

### **Sub-Group Analyses**

The primary and secondary endpoints will be analyzed without regard to age and sex given the narrow inclusion criteria for age and the lack of evidence to suggest sex-based differences in glycemic control among youth with T1D. Race/ ethnicity will not be factored in as the study will not have a large enough sample size and sufficient power to stratify findings based on race/ethnicity.

### **Tabulation of Individual participant Data**

Individual participant data will be listed by measure and time point.

### **Exploratory Analyses**

Thematic analysis of qualitative data from interview transcripts will be performed by two research team members. Initial codes will be developed independently by these team members who will then generate a second-cycle list of codes. All team members will then apply the revised coding framework to the transcription. The team will meet to reach consensus on the final codes and identify dominant themes.

## **8.5 Sample Size**

As this is a pilot study, we plan to enroll up to 20 parent-child dyads. We anticipate low dropout rates, but do plan to enroll new subjects to keep the total number of subjects at up to 20 in case of attrition. If there is a sufficient number of new subjects enrolled to replace those that drop out, a new SMA group will be created so that newly enrolled subjects will be able to start the intervention from the baseline visit.

## **8.6 Measures to Minimize Bias**

Not applicable

## **Section 9: Data Quality and Oversight**

### **9.1 Study Team Quality Assurance and Quality Control**

Study staff will perform internal quality management of study conduct, data and biological specimen collection, documentation and completion. An individualized quality management plan will be developed to describe the study's quality management.

Quality control (QC) procedures will be implemented beginning with the data entry system and data QC checks that will be run on the database will be generated. Any missing data or data anomalies will be communicated to the site(s) for clarification/resolution.

Following written Standard Operating Procedures (SOPs), the study staff will verify that the clinical trial is conducted and data are generated and biological specimens are collected, documented (recorded), and reported in compliance with the protocol, International Conference on Harmonization Good Clinical Practice (ICH GCP), and applicable regulatory requirements (e.g., Good Laboratory Practices (GLP), Good Manufacturing Practices (GMP)).

The investigational site will provide direct access to all trial related sites, source data/documents, and reports for the purpose of monitoring and auditing by the sponsor, and inspection by local and regulatory authorities.

## **9.2 Data Safety and Monitoring Plan**

Safety oversight will be under the direction of the PI without a Data Safety Monitoring Board.

Clinical site monitoring is conducted to ensure that the rights and well-being of trial participants are protected, that the reported trial data are accurate, complete, and verifiable, and that the conduct of the trial is in compliance with the currently approved protocol/amendment(s), with International Conference on Harmonization Good Clinical Practice (ICH GCP), and with applicable regulatory requirement(s).

- The PI will direct the conduct of site monitoring on-site prior to the start of the study and will direct review 100% of the data.
- Independent audits will not be conducted.

## **Section 10: Ethical Considerations**

### **10.1 Ethical Standard**

The study team will ensure that this study is conducted in full conformity with the Regulations for the Protection of Human Subjects of Research codified in 45 Part 46 of the Code of Federal Regulations, Children's National Policies and Procedures and Good Clinical Practices.

### **10.2 Institutional Review Board (IRB)**

The protocol, informed consent form(s) and all participant materials will be submitted to the Children's National IRB for review and approval. Approval of both the protocol and the consent form will be obtained before any participant is consented. Any change to the protocol, consent, and participant information sheets or letters will require IRB approval before implementation and use. The IRB will determine whether previously consented participants need to be re-consented and whether consent of more than one parent is required for minors.

The IRB will be notified of study team updates via an amendment. DSMB Reports will be submitted at the time of the continuing review or with another applicable IRB transaction. Other study events (e.g., protocol deviations, data monitoring reports) will be submitted per the Children's National IRB Reportable Events Module.

### **10.3 Maintaining Subject Privacy**

To protect privacy, identification numbers will be used to identify all study information, and only authorized study personnel will have access to study records, with the permission of the PI. When participants fill out questionnaires, their responses will be paired with this unique number instead of their names. Each participant's identifying data will be separated from the study data and all clinically- relevant and study data will be stored in a password-protected database, on a password-protected computer, or in a locked filing cabinet in a locked office. Information about subjects will not be accessible to any non-authorized study personnel without the written consent of the subject. SMA sessions will occur as a group with other participants and caregivers, but each youth and their caregiver will meet with the pediatric endocrinologist individually and have the opportunity to discuss sensitive information in private.

### **10.4 Maintaining Study Data Confidentiality**

Participant confidentiality and privacy is strictly held in trust by the participating investigators, their staff, and the sponsor(s) and their interventions. This confidentiality is extended to cover clinical information relating to participants. Therefore, the study protocol, documentation, data, and all other information generated will be held in strict confidence. No information concerning the study or the data will be released to any unauthorized third party without prior written approval of the sponsor. All research activities will be conducted in as private a setting as possible.

[name] assures that informed consent is obtained prior to performing any research procedures, that all subjects meet eligibility criteria, and that the study is conducted according to the IRB-approved research plan. Study data are accessible at all times for the PI to review. The PI review(s) study conduct on a weekly basis. The PI review(s) AEs individually in real-time and in aggregate on a twice weekly basis. The PI review(s) serious and reportable adverse events (SAEs) in real-time. The PI ensures all protocol deviations, AEs, and SAEs are reported to the IRB according to the applicable regulatory requirements.

The sponsor representatives and regulatory authorities (e.g., IRB, OHRP) may inspect all documents and records required to be maintained by the investigator. The clinical study site will permit access to such records.

The study participant's contact information and data will be securely stored at Children's National Hospital for internal use during the study. At the end of the study, all records will continue to be kept in a secure location for as long a period as dictated by the reviewing IRB, Institutional policies, or FDA requirements. The research data will not include the participant's contact or identifying information. Rather, individual participants and their research data will be identified by a unique study identification number. The

study data entry and study management systems used by research staff will be secured and password protected. At the end of the study, all study databases will be archived at Children's National.

